4.1.2 Run-in Visit (Visit 2, Week -1)

Visit 2 should take place 3 to 5 days prior to Visit 3. Prior to this visit, patients are to have fasted overnight (at least 10 hours). Patients are to refrain from alcohol intake and intense exercise 24 hours prior to each visit and recommend not to use tobacco/nicotine within 12 hours prior to each visit. Patients should delay administering their morning dose of metformin or metformin/sulfonylurea on the morning of the study site visit. The following will be performed during this visit:

- Concomitant medications (including over the counter and herbal/nutritional supplements) will be reviewed.
- Urinary pregnancy test for all female patients (WOCBP only) will be performed.

Double tracer OGTT will be performed.

- Blood samples will be collected for the following assessment:
 - HbA1c
 - FPG and ketones
 - Fasting serum lipid concentrations (total cholesterol LDL cholesterol, HDL cholesterol, non-HDL cholesterol, and triglycerides)
 - Serum pregnancy test for all female patients (WOCBP only) if urine pregnancy test result is positive
 - Serum creatinine (estimated GFR)

- AEs will be reviewed.
- Patient instructions will be provided.
- Glucose meter and supplies will be provided.
- 7-point self-monitored blood glucose (SMBG) instructions will be provided.

Study site personnel will instruct patients to take metformin or metformin/sulfonylurea (with food) after the study visit is complete.

4.1.3 Randomization and Baseline Visit (Visit 3, Week 0)

Visit 3 should take place 3 to 5 days after Visit 2. Prior to this visit, patients are to have fasted overnight (at least 10 hours). Patients are to refrain from alcohol intake and intense exercise 24 hours prior to each visit and recommend not to use tobacco/nicotine within 12 hours prior to each visit. Patients should delay administering their morning dose of metformin on the morning of the study site visit. The following will be performed during this visit:

- Randomization criteria will be verified.
- Body weight will be measured.
- Vital signs (sitting systolic and diastolic BP and HR) will be assessed.
- Waist and hip circumference will be measured.
- Concomitant medications (including over-the-counter and herbal/nutritional supplements) will be reviewed.
- Urinary pregnancy test for all female patients (WOCBP only) will be performed.
- Patients will perform 7-point SMBG prior to the visit.

- AEs will be reviewed.
- Blood samples will be collected **prior to glucose turnover study and administration of study medication** for the following assessments:
 - FPG and ketones
 - Serum pregnancy test for all female patients (WOCBP only) if urine pregnancy test result is positive
- Glucose turnover study will be initiated.
- During the baseline infusion period of the glucose turnover study, prior to Time 0 collection, the following will be performed:
 - Diet and exercise counselling will be provided.
 - 7-point SMBG will be reviewed and recorded.
 - Patients will be randomly assigned to 1 of 3 treatment groups (while continuing on metformin therapy):
 - saxagliptin 5 mg + dapagliflozin 10 mg;
 - dapagliflozin 10 mg + placebo for saxagliptin;
 - placebo for dapagliflozin + placebo for saxagliptin.
 - Study medication will be dispensed during Time 0 of glucose turnover study. Study site personnel will monitor administration of study medication. Glucose turnover study will be completed.

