4. STUDY PLAN AND TIMING OF PROCEDURES

[Table 1](#) presents the schedule of assessments for this study.

Table 1 Study Plan

Evaluation	Screening	Run-in	Treatment Period					End of treatment/Early Termination or Rescue ^a
			1	2	3	4	5	
Visit	1	2	3	4	5	6	7	8
Week	-2	-1	0	4	8	12	15	16
Relative to Randomization (days)	-14	-9	R	28	56	84	103	112
Visit Window (±days)	(+7)	(±4^b)	0	(±5)	(±5)	(±5)	(±5)	(±4^b)
Obtain Informed Consent	X							
Review Medical and Surgical History	X							
Review Eligibility Criteria (Inclusion/Exclusion Criteria)	X							
Review Randomization Criteria			X					
Verify Patient Fasted 10 Hours	X	X	X	X	X	X	X	X
Complete Physical Examination	X							X
Brief Physical Assessment (at the Investigator's discretion)				X	X	X	X	
Body Weight	X		X	X	X	X	X	X
Height	X							
Body Mass Index	X							X
Vital signs (reclining/standing BP and HR)	X		X	X	X	X	X	X
Waist and Hip Circumference	X		X	X	X	X		X
12-lead ECG	X							X
Review Concomitant Medications ^c	X	X	X	X	X	X	X	X
Provide Diet and Exercise Counseling	X		X		X			
Verify IP Compliance				X	X	X	X	X
Dispense Study Medication			X	X	X	X		
Provide Glucose Meter and Supplies/Instructions for 7-point SMBG		X						
Perform 7-point SMBG Prior to Site Visit			X ^d	X	X	X	X ^d	X

Evaluation	Screening	Run-in	Treatment Period					End of treatment/Early Termination or Rescue ^a
	1	2	3	4	5	6	7	8
Visit	-2	-1	0	4	8	12	15	16
Week	-14	-9	R	28	56	84	103	112
Relative to Randomization (days)	(+7)	(±4 ^b)	0	(±5)	(±5)	(±5)	(±5)	(±4 ^b)
Review 7-point SMBG and hypoglycemia episodes			X	X	X	X	X	X
Collect Glucose Meter/Unused Supplies								X
Collect unused study medication								X
Dispense Rescue Medication (if needed)					X	X	X	
Assess AEs		X	X	X	X	X	X	X
Pregnancy Test (urine and serum if urine test positive) WOCBP only	X	X	X	X	X	X	X	X
Clinical Chemistry, Hematology ^c	X				X			X
eGFR and Serum Creatinine	X	x	x	x	X	x	x	X
HbA1C	X	X		X	X	X	X	X
FPG/ketones	X	X	X	X	X	X	X	X
Fasting Serum Lipids ^f	X	X			X		X	X
Thyroid function (TSH and T4)	X							
FFA	X							X
Urinalysis ^e	X							X
Double Tracer OGTT ^h with IC		X						X
Glucose Turnover Study ⁱ			X				(X) ^j	
DEXA	X							X

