4.1.1 Screening Visit (Visit 1, Week -2)

At Screening, informed consent will be obtained prior to performing any protocol-required procedures. Patients will be assessed to ensure that they meet eligibility criteria. Patients who do not meet these criteria must not be enrolled in the study.

Screening procedures should be scheduled for at least 1 day later than the day of informed consent signature if the patient is not in a fasting state on the consent date.

The following will be performed during this visit:

- The patient's complete medical and surgical history will be recorded.
- Inclusion and exclusion criteria will be verified.
- A complete physical exam will be conducted.
- Body weight and height will be measured.
- BMI will be calculated.
- Vital signs (reclining and standing systolic and diastolic BP and heart rate [HR]) will be measured.
- Waist and hip circumference will be measured.
- 12-lead ECG will be performed.
- All prior medications (prescription medications within 3 months) and concomitant medications (including over the counter and herbal/nutritional supplements) will be reviewed.
- Diet and exercise counselling will be provided.
- Urinary pregnancy test for all female patients (WOCBP only) will be performed.
- Blood samples will be collected for the following assessments:
 - Chemistry and hematology
 - Serum creatinine (estimated GFR)
 - HbA1c
 - Fasting plasma glucose (FPG) and ketones

- Fasting serum lipid concentrations (total cholesterol, low-density lipoprotein [LDL] cholesterol, high-density lipoprotein [HDL] cholesterol, non-HDL cholesterol, and triglycerides)
- Thyroid function (TSH and T4)
- FFA
- Serum pregnancy test for all female patients (WOCBP only) if urine pregnancy test result is positive
- Urine will be collected for urinalysis.
- DEXA scan will be performed.

Individuals will be screen failed if results of any laboratory test are abnormal and clinically significant as judged by the Investigator or medical monitor. Individuals may qualify for study run-in following an acceptable repeated lab result for an initially abnormal result as judged by the Investigator).

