Prior to these visits, patients are to have fasted overnight (at least 10 hours). Patients are to refrain from alcohol intake and intense exercise 24 hours prior to each visit and recommend not to use tobacco/nicotine within 12 hours prior to each visit. Patients should delay administering their morning dose of metformin or metformin/sulfonylurea and study medication on the morning of the study site visits. Patients should bring their metformin or metformin/sulfonylurea and study medication with them to the study site and will self-administer study medication as directed by study site personnel.

The following will be performed during these visits:

- A brief physical assessment may be conducted at the Investigator's discretion.
- Body weight will be measured.
- Vital signs (reclining and standing systolic and diastolic BP and HR) will be assessed.
- Waist and hip circumference will be measured (Visits 4, 5, and 6).
- Concomitant medications (including over-the-counter and herbal/nutritional supplements) will be reviewed.
- Diet and exercise counselling will be provided (Visit 5 only).
- Study medication compliance will be reviewed.
- Patients will perform 7-point SMBG prior to visits.
- 7-point SMBG will be reviewed and recorded.
- Rescue medication will be dispensed (if needed, see [Table 2](#)).
- AEs will be reviewed.

- Urinary pregnancy test for all female patients (WOCBP only) will be performed.
- Blood samples will be collected **prior to administration of study medication** for the following assessments:
 - Chemistry and hematology (Visit 5 only)
 - Serum creatinine (calculated creatinine clearance; Cockcroft-Gault formula; Visit 5 only)
 - HbA1c
 - FPG and ketones
 - Fasting serum lipid concentrations (Visits 5 and 7 only)
 - Serum pregnancy test for all female patients (WOCBP only) if urine pregnancy test result is positive
 - Serum creatinine (estimated GFR)
 -
- Glucose turnover study will be performed. **Study medication will be ingested at the end of the 3-hour tracer equilibration period.**

Study site personnel will instruct patients to take IP and metformin (with food) after the study visit is complete.

4.2.2 End of Treatment Period Visit/Early Termination during Treatment Period or Rescue (Visit 8, Week 16)

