5.2.4 Vital signs

Vital sign measurements in this study will include reclining (for 5 minutes) and standing (for 2 minutes) systolic and diastolic BP and HR. Vital signs should be measured at every visit after the patient reclines for approximately 5 minutes and after standing for 2 minutes.

Blood pressure measurement will be performed with the Dynamap. An appropriate-sized cuff (cuff bladder encircling at least 80% of the arm) should be used to ensure accuracy. At least 2 measurements should be made at least 30 seconds apart and the average recorded. The same arm should be used for all BP measurements during the study.

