8. STATISTICAL ANALYSES

8.1 Statistical considerations

All personnel involved with the analysis of the study will remain blinded until database lock and protocol violators identified at the end of the 16-week randomized treatment period.

The primary efficacy measure of EGP will be derived by the Investigator. The remaining statistical analysis of this study will be performed by the Investigator.

Baseline: Unless otherwise specified, baseline refers to the last measurement collected prior to the first dose of study medication at the Randomization Visit. For parameters derived from the glucose turnover study and OGTT, several time points prior to the first dose of study medication may be averaged to calculate baseline.

All collected data will be listed. A comprehensive Statistical Analysis Plan (SAP) is described in the following sections.

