8.4 Outcome measures for analyses

The mean values will be compared between the treatment groups for the following measures:

1. Post-IP minus pre-IP EGP during glucose turnover study at Week 15.
2. Post-IP minus pre-IP EGP during glucose turnover study at Week 0 and the change from Week 0 to Week 15.
3. Pre-IP EGP during glucose turnover study at Week 15 and the change from Week 0 to Week 15.

4. Pre-glucose load EGP during the OGTT at Week 16 and the change from Week -1 to Week 16.
5. Change from Week -1 to Week 16 in post-glucose load EGP during the OGTT.
6. Change from Week -1 to Week 16 in Rd and Ra during OGTT.
7. Change from Week 0 to Week 16 in HbA1c.
8. Change from Week 0 to Week 15 in pre-IP plasma glucose during glucose turnover study.
9. Change from Week -1 to Week 16 in pre-glucose load FPG and post-glucose load PPG during the glucose turnover study.
10. Change from Week -1/0 to Week 15/16 in fasting plasma glucagon, C-peptide, and insulin during the glucose turnover study and OGTT.
11. Change from Week -1/0 to Week 15/16 in plasma glucagon, C-peptide, and insulin during the glucose turnover study and OGTT.
12. Change from Week 0 to Week 15 in post-IP minus pre-IP plasma glucagon, C-peptide, and insulin during the glucose turnover study.
13. Change from Week -1 to Week 16 in insulin secretion, beta cell function, and insulin sensitivity during OGTT.
14. Change in glucose oxidation and lipid oxidation during the baseline of the glucose turnover study, during the baseline of the OGTT, and post-glucose load during the OGTT.
15. Change in plasma ketones during the baseline of the glucose turnover study and OGTT.
16. Change from Week 0 to Week 15 in pre-IP, post-IP, and post-IP minus pre-IP in counterregulatory hormones during glucose turnover study.
17. Change from Week -2 to Week 16 in body weight and BMI; and percent body fat and fat distribution calculated from the DEXA scans.
18. Change from Week -1 to Week 16 in plasma GLP-1, GIP, and FFA during OGTT.
19. Change from Week -2 to Week 16 in FFA.
20. Change from Week 0 to Week 16 in waist to hip ratio, BP, and lipids.

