8.5.2 Analysis of the secondary and exploratory variables

The continuous secondary endpoints will be analyzed using a repeated measures model when the endpoints are collected at visits in addition to Week 16. A longitudinal repeated measures analysis (using a MIXED model) for the change from baseline at Week 16, with terms for treatment group, baseline HbA1c subgroup ($\leq 8.5\%$ versus $> 8.5\%$), baseline treatment (metformin versus metformin/sulfonylurea) baseline value, time (each relevant visit), the interaction of treatment and time, and the interaction of baseline value and time in the model. Point estimates and 95% confidence intervals will be calculated for the adjusted mean changes within each treatment group as well as for the differences in adjusted mean changes between treatment groups.

The continuous secondary endpoints will be analyzed using an ANCOVA model like the primary endpoint when the endpoints are collected at baseline visit (Visit 3) and Week 16 only.

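### The Visit 3 and Visit 8 lists take sitting blood pressure where Table 1 and 5.2.4 require reclining and standing readings; if the lists are followed, changes to Weeks 4–15 mix postures and randomisation and Week 16 have no orthostatic pair

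*Combined protocol and SAP*

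**What the plan says.** Two sets of instructions on posture stand in the current text.

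- **Visit lists.** Screening (4.1.1): "Vital signs (reclining and standing systolic and diastolic BP and heart rate [HR]) will be measured". Randomisation (4.1.3): "Vital signs (sitting systolic and diastolic BP and HR) will be assessed". Visits 4 to 7 (4.2.1): "Vital signs (reclining and standing systolic and diastolic BP and HR) will be assessed". Visit 8 (4.2.2), whose heading also covers early termination and rescue, repeats the sitting wording of 4.1.3.
- **Study plan and measurement section.** The Table 1 row begins "Vital signs (reclining/standing BP and HR" and is marked at Visit 1 and Visits 3 to 8. Section 5.2.4 states: "Vital signs should be measured at every visit after the patient reclines for approximately 5 minutes and after standing for 2 minutes".

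On the analysis side, item 20 of 8.4 lists "Change from Week 0 to Week 16 in waist to hip ratio, BP, and lipids" and names no posture. The matching objective in 2.4 is exploratory and covers change within each group as well as between groups. Section 8.1 says that, unless otherwise specified, "baseline refers to the last measurement collected prior to the first dose of study medication at the Randomization Visit". Section 8.5.2 says: "The continuous secondary endpoints will be analyzed using a repeated measures model when the endpoints are collected at visits in addition to Week 16". Section 8.5.5 plans standard tabulations of vital signs. Section 6.5 includes volume depletion, with hypotension, among the events of special interest.

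**The concern.** At Visits 3 and 8 the visit list and the study plan ask for different readings, so a site that follows one departs from the other. If the visit lists are followed, Week 0 is a sitting value while the next four visits give reclining and standing values. A change from Week 0 to any of those visits then contains a difference between postures as well as any change over time. That affects the within-group changes, which 2.4 sets out to explore, and the safety tabulations by visit.

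The second stake is orthostatic information. Volume depletion and hypotension are of special interest, and the note to exclusion criterion 8 asks for careful monitoring of volume status in eligible patients with heart failure. Under the visit lists, the two visits that open and close treatment have no reclining/standing pair.

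**Working it through.** The plan states no figure here and nothing can be recomputed. The check sets the instructions side by side and traces each comparison.

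| Visit (week) | Visit list | Table 1 and 5.2.4 |
|---|---|---|
| 1 (−2) | reclining and standing | reclining and standing |
| 3 (0) | **sitting** | reclining and standing |
| 4, 5, 6, 7 (4, 8, 12, 15) | reclining and standing | reclining and standing |
| 8 (16, early termination, rescue) | **sitting** | reclining and standing |

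**Step 1: the listed outcome, Week 0 to Week 16.** Under the visit lists it is sitting to sitting. Under Table 1 and 5.2.4 it is reclining to reclining or standing to standing. It is matched either way, provided one instruction is followed at both visits.

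**Step 2: changes to Weeks 4, 8, 12 and 15 under the visit lists.** Write s for sitting and r for the reclining (or standing) reading. For visit v,

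BP_v(r) − BP_0(s) = [BP_v(s) − BP_0(s)] + [BP_v(r) − BP_v(s)].

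The first bracket is the like-for-like change and the second is the posture difference at that visit. The second bracket enters at Visits 4, 5, 6 and 7, which is 4 of the 5 visits after randomisation. The documents give no value for it, so its size and sign are left open.

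**Step 3: between-group comparisons.** At each visit all groups are measured in the same posture. The baseline term BP_0(s) has the same expectation in every group by randomisation. The between-group contrast therefore remains like for like in expectation. The problem lies in the within-group changes.

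**Step 4: orthostatic pairs under the visit lists.** Pairs exist at Visit 1 and at Visits 4 to 7, and not at Visit 3 or Visit 8. From the days in Table 1, the last pre-dose pair falls 14 days before randomisation. The last scheduled on-treatment pair falls 112 − 103 = 9 days before Week 16.

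**Step 5: the same checks under Table 1 and 5.2.4.** All seven visits marked for vital signs use one protocol, so steps 2 and 4 raise no problem. One gap remains: each visit then yields two blood pressures, and item 20 of 8.4 does not say which of them is the outcome.

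**The case against.** A reader might infer that the planned blood pressure outcome itself mixes postures. The documents do not support that: the only listed outcome runs from Week 0 to Week 16, and step 1 shows it is matched under either instruction.

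A reader might also infer that orthostatic change has no baseline at all. That is not supported either. Screening takes a reclining and standing pair before any dose, and under the definition in 8.1 it can reasonably serve as the last pre-dose value. A change from screening to Week 15 could still be calculated.

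The repeated-measures argument is limited too. The sentence in 8.5.2 names secondary endpoints and blood pressure is exploratory, although the section heading covers both. If the model is applied and time is categorical, as its terms suggest, a posture shift at Visits 4 to 7 is taken up mainly in those visits' own means and does not move the Week 16 change.

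Finally, 4.1 and 4.2 refer procedures and visits to Table 1, and the last line of 4.2.2 sends early-discontinued and rescued patients to the table. On that reading the sitting bullets are drafting slips with no effect on the data. No orthostatic endpoint is listed in 8.4 and no orthostatic analysis in 8.5.5.

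All of this stands, and it confines the point to what happens if staff work from the visit lists. It does not remove the contradiction: staff at Visits 3 and 8 have an explicit instruction to take sitting readings, and no stated order of precedence tells them to set it aside.

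**Conclusion.** The contradiction is real, sits in operative text, and is minor. It concerns two of the seven visits at which vital signs are scheduled. The consequences depend on the visit lists being followed. In that case:

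- changes from Week 0 mix postures at Weeks 4, 8, 12 and 15, in the safety tabulations and in a repeated-measures model if 8.5.2 is applied to blood pressure;
- there is no reclining/standing pair at randomisation, nor at Week 16 or an early-termination visit run from the 4.2.2 list, so orthostatic change from randomisation to end of treatment cannot be computed.

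The missing posture in item 20 of 8.4 matters if Table 1 and 5.2.4 are followed, because the choice between two readings would then be left until after the data are collected. The primary endpoint and the between-group contrasts are not put in doubt. The size of the posture shift cannot be stated from the documents.

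**What to change.** Reconcile the vital-sign bullets in 4.1.3 and 4.2.2 with Table 1 and 5.2.4, so that every visit with vital signs uses the same posture protocol. In item 20 of 8.4, name the posture used for the blood pressure outcome. If readings have already been taken under the conflicting text, record the posture actually used so that changes can be restricted to matching pairs.

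The cost is two reworded bullets and one added phrase. At Visits 3 and 8 the timings in 5.2.4 imply about 5 + 2 = 7 minutes of reclining and standing per visit.

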4.2 Treatment Period

After the Randomization visit (Visit 3), patients will complete study visits at 1- to 4-week intervals according to the Study Plan (Table 1) until the end of the randomized treatment period (Visit 8, Week 16). During Weeks 6 to 16 of the double-blind treatment period of the trial, patients may be eligible for the addition of open-label rescue medication to their blinded treatment regimen in order to treat ongoing hyperglycemia, based upon established laboratory FPG values and repeat, confirmatory FPG criteria (Table 2).

Table 2 Criteria for Initiation of Rescue Therapy During the Randomized Treatment Period

Visit Period	Central Laboratory FPG
Week 6	FPG >270 mg/dL (15.0 mmol/L)
After Week 6 to Week 12 (excluding Week 12)	FPG >240 mg/dL (13.3 mmol/L)
After Week 12 to Week 16 (excluding Week 16)	FPG >200 mg/dL (11.1 mmol/L)

Abbreviation: FPG fasting plasma glucose.

Patients with a laboratory FPG value meeting the lack of glycemic control criterion at a pre-specified visit will be scheduled for a Follow-up Visit (within 3 to 5 days) to obtain a second laboratory FPG value and review the patient's glucose meter readings. If the repeat laboratory FPG value still meets the criterion, the patient must be rescued. Patients should continue receiving study medication while receiving rescue therapy. Patients who meet rescue criteria in the double-blind treatment period must first complete an OGTT and the Visit 8/End of Treatment procedures, including a glucose turnover study and DEXA scan, before receiving open-label rescue medication, to ensure that important trial endpoint measurements are collected. Rescued patients will be given open-label antidiabetic rescue medication in accordance with the approved product label in the applicable country at the discretion of the Investigator, in addition to their double-blinded study medication. Rescued patients will then continue in the double-blind treatment period according to their original visit schedule.

Following initiation of open-label rescue medication, rescued patients should have their glycemic response to the rescue medication evaluated by the Investigator. At the end of the study or at early termination, rescued patients should undergo a double tracer OGTT, glucose turnover study, and DEXA scan.

4.2.1 Treatment Period visits (Visits 4 to 7, Weeks 4, 8, 12, and 15)

Prior to these visits, patients are to have fasted overnight (at least 10 hours). Patients are to refrain from alcohol intake and intense exercise 24 hours prior to each visit and recommend not to use tobacco/nicotine within 12 hours prior to each visit. Patients should delay administering their morning dose of metformin or metformin/sulfonylurea and study medication on the morning of the study site visits. Patients should bring their metformin or metformin/sulfonylurea and study medication with them to the study site and will self-administer study medication as directed by study site personnel.

The following will be performed during these visits:

- A brief physical assessment may be conducted at the Investigator's discretion.
- Body weight will be measured.
- Vital signs (reclining and standing systolic and diastolic BP and HR) will be assessed.
- Waist and hip circumference will be measured (Visits 4, 5, and 6).
- Concomitant medications (including over-the-counter and herbal/nutritional supplements) will be reviewed.
- Diet and exercise counselling will be provided (Visit 5 only).
- Study medication compliance will be reviewed.
- Patients will perform 7-point SMBG prior to visits.
- 7-point SMBG will be reviewed and recorded.
- Rescue medication will be dispensed (if needed, see [Table 2](#)).
- AEs will be reviewed.

- Urinary pregnancy test for all female patients (WOCBP only) will be performed.
- Blood samples will be collected **prior to administration of study medication** for the following assessments:
 - Chemistry and hematology (Visit 5 only)
 - Serum creatinine (calculated creatinine clearance; Cockcroft-Gault formula; Visit 5 only)
 - HbA1c
 - FPG and ketones
 - Fasting serum lipid concentrations (Visits 5 and 7 only)
 - Serum pregnancy test for all female patients (WOCBP only) if urine pregnancy test result is positive
 - Serum creatinine (estimated GFR)
 -
- Glucose turnover study will be performed. **Study medication will be ingested at the end of the 3-hour tracer equilibration period.**

Study site personnel will instruct patients to take IP and metformin (with food) after the study visit is complete.

4.2.2 End of Treatment Period Visit/Early Termination during Treatment Period or Rescue (Visit 8, Week 16)

Prior to this visit, patients are to have fasted overnight (at least 10 hours). Patients are to refrain from alcohol intake and intense exercise 24 hours prior to each visit and recommend not to use tobacco/nicotine within 12 hours prior to each visit. Patients should delay administering the morning dose of metformin and study medication on the morning of the visit and bring metformin and study medication to the study site visit.

The following procedures will be conducted:

- A complete physical examination will be conducted.
- Body weight will be measured.
- BMI will be calculated.
- Vital signs (sitting systolic and diastolic BP and HR) will be assessed.
- Waist and hip circumference will be measured.
- 12-lead ECG will be performed.
- Concomitant medications (including over-the-counter and herbal/nutritional supplements) will be reviewed.

- Study medication compliance will be reviewed.
- Patient will perform 7-point SMBG prior to Visit 8.
- 7-point SMBG will be reviewed and recorded.
- Glucose meter and supplies will be collected.
- Unused study medication will be collected.
- AEs will be assessed.
- Urinary pregnancy test for all female patients (WOCBP only) will be performed.
- Blood samples will be collected **prior to administration of study medication** for the following assessments:
 - Chemistry and hematology
 - Serum creatinine (calculated creatinine clearance; Cockcroft-Gault formula)
 - HbA1c
 - FPG and ketones
 - Fasting serum lipid concentrations
 - FFA
 - Serum pregnancy test for all female patients (WOCBP only) if urine pregnancy test result is positive
 - Serum creatinine (estimated GFR)
 -
- Urine will be collected for urinalysis.
- Double tracer OGTT will be performed (approximately 10 days after glucose turnover study).
- DEXA scan will be performed or can be performed on a separate day.

If a patient is early discontinued or rescued, see visits 15 and 16 in Table for procedures.

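### Table 2 sets no rescue threshold for the scheduled Week 12 fasting glucose (Visit 6)

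*Combined protocol and SAP*

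**What the plan says.** Section 4.2 opens the rescue period: "During Weeks 6 to 16 of the double-blind treatment period of the trial, patients may be eligible" for open-label rescue. Table 2 then gives three FPG criteria:

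- Row 1, Week 6: >270 mg/dL.
- Row 2, "After Week 6 to Week 12 (excluding Week 12": >240 mg/dL.
- Row 3, "After Week 12 to Week 16 (excluding Week 16": >200 mg/dL.

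The trigger is tied to scheduled visits: "Patients with a laboratory FPG value meeting the lack of glycemic control criterion at a pre-specified visit" are recalled within 3 to 5 days for a second FPG. Rescue is then mandatory: "If the repeat laboratory FPG value still meets the criterion, the patient must be rescued". A glucose turnover study, an OGTT and the Visit 8 procedures come first, "to ensure that important trial endpoint measurements are collected".

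Table 1 puts Visit 6 at Week 12, Day 84, with a window of ±5 days and an FPG sample. It marks the row "Dispense Rescue Medication (if needed" at Visits 5, 6 and 7. Section 4.2.1, which covers Visits 4 to 7, says "Rescue medication will be dispensed (if needed, see" and points to Table 2. Section 7.7.2 mentions FPG rescue criteria without giving values. No Week 12 threshold appears anywhere else.

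**The concern.** Row 2 expressly stops short of Week 12 and row 3 begins after it. A scheduled visit inside the rescue period, with an FPG drawn, therefore has no criterion. Taken literally, even an FPG of 300 mg/dL at Week 12 triggers nothing.

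The first stake is patient safety. The trial has a double-placebo arm and admits patients with HbA1c up to 11.0%, and Table 2 is the rule meant to catch persistent hyperglycemia.

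The second is the analysis. Section 8.5 excludes values collected after rescue, and 8.5.1 removes a rescued subject from the primary analysis. An undefined rescue rule therefore leaves part of the analysis data undefined.

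**Working it through.** The plan states no figure to reproduce here; the check is one of coverage. The mmol/L equivalents printed in Table 2 are correct: dividing by 18.016, 270, 240 and 200 mg/dL give 14.99, 13.32 and 11.10.

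**1. By visit label.** Visits and days are from Table 1, rows from Table 2.

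| Visit | Week | Day | Table 2 row |
|---|---|---|---|
| 4 | 4 | 28 | none (before the rescue period) |
| 5 | 8 | 56 | row 2, >240 |
| 6 | 12 | 84 | none |
| 7 | 15 | 103 | row 3, >200 |
| 8 | 16 | 112 | none (excluded by row 3; end of treatment) |

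No Week 6 visit is scheduled, so row 1 matches no planned sample. The scheduled FPGs with a threshold are those at Visits 5 and 7: 103 − 56 = 47 days apart. A patient with a high value at Visit 6 waits 103 − 84 = 19 days for the next scheduled trigger.

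**2. By calendar day.** Week 12 is Day 12 × 7 = 84, and the Visit 6 window is 84 ± 5, or Days 79 to 89. Days 79-83 fall in row 2 (>240), Day 84 in no row, and Days 85-89 in row 3 (>200). An FPG of 220 mg/dL would trigger nothing on Day 83 and a recall on Day 85. Visits 5 and 7 do not have this problem: 56 ± 5 is Days 51-61, inside row 2, and 103 ± 5 is Days 98-108, inside row 3.

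**3. Repeat test.** The repeat can cross the boundary. Take 245 mg/dL on Day 82 and 220 mg/dL on Day 86, 4 days later. The repeat confirms under >200 but not under >240, and Table 2 does not say which applies.

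**4. Where the neighbouring rows disagree.** Above 240 both call for rescue; at 200 or below neither does. The disputed band is above 200 and up to 240 mg/dL, 240 − 200 = 40 mg/dL wide.

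**5. What follows for the data.** Take a patient in that band.

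- *Threshold >200 at Week 12.* The repeat falls on Days 87-89 (84 + 3 to 84 + 5). Table 1 footnote j places the pre-rescue turnover study 5 to 14 days before the OGTT. If that study is done on the day of the repeat (an assumption), the pre-rescue tests end between Day 87 + 5 = 92 and Day 89 + 14 = 103. Rescue can then begin before Visit 7, and later values, such as the Visit 7 HbA1c, are lost under 8.5 from the repeated-measures analysis in 8.5.2.
- *No trigger at Week 12, or >240.* The next scheduled trigger is Visit 7, whose turnover study is done at that visit. The repeat falls on Days 106-108 (103 + 3 to 103 + 5), and the Visit 8 procedures, nominally Day 112, must precede rescue. The Week 15 values are then pre-rescue and are kept under 8.5.

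A patient confirmed above 200 at Week 12 but not at Week 15 is rescued on one reading and never rescued on the other, so inclusion under 8.5.1 differs. For a patient confirmed above 200 at both visits, the timing differs. Whether inclusion also differs depends on how 8.5 (use values before rescue) is reconciled with 8.5.1 (drop rescued subjects).

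**The case against.** The likely intent is visible. Excluding Week 12 from row 2 reads most naturally as handing it to the next, stricter row. A sensible site would rescue a patient confirmed above 240 mg/dL, since that exceeds both neighbouring thresholds. This supports the proposed fix, but the text does not say it, and the disputed band remains.

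On a calendar reading only Day 84 is uncovered. That narrows the gap but makes the threshold depend on the appointment date. A single site does not remove that inconsistency.

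A reader might count the rescue-dispensing marks in Table 1 and say that one of three rescue visits lacks a threshold. The documents do not support that count. The marks are for dispensing, and a Visit 6 FPG cannot lead to rescue at Visit 6, because a repeat FPG and the pre-rescue studies must come first. The Visit 6 mark may serve an earlier trigger. The point rests instead on the Weeks 6 to 16 eligibility, the scheduled FPG and the reference in 4.2.1.

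The effect is probably small, and this objection stands. Section 1.2 says the HbA1c range was chosen with a low chance of rescue in mind. Section 8.2 already allows 10% for early termination, rescue or a missing Week 16 assessment. Both primary arms receive dapagliflozin, which section 1.1 credits with lowering FPG by about 30 mg/dL. Patients still above 200 may therefore sit more often in the 11-patient placebo arm, which is only an inference. EGP is measured before rescue in any case, and 8.5.4 allows an optional all-data sensitivity analysis.

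**Conclusion.** The point holds: Table 2 is wrong as written for Week 12, and the severity is minor. By visit label, no Week 12 FPG triggers rescue and 47 days separate the scheduled FPGs that have a threshold. By calendar day, the rule changes twice within one visit window. The practical disagreement is confined to values above 200 and up to 240 mg/dL. There the reading can alter whether and when rescue happens, the secondary values retained and, for some patients, inclusion in the primary analysis. Against the 19 evaluable patients planned per primary arm, each patient is 1/19, about 5%, of an arm.

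Two stronger readings go too far. A reader might infer that the gap biases the treatment comparison. No bias is shown: the rule applies alike to blinded arms, and the documents give no FPG distribution from which to estimate how many patients are affected. A reader might also infer that primary-analysis status changes solely for patients who fall back to 200 or below by Week 15. That is more exact than the text allows, because 8.5 and 8.5.1 do not settle the status of a patient whose Week 15 EGP precedes rescue.

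**What to change.** Change row 3 of Table 2 to run from Week 12 up to, but excluding, Week 16, at >200 mg/dL. This fits row 2's express exclusion of Week 12. If the clinical team intends >240 mg/dL at Week 12, extend row 2 to include it instead.

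Add one footnote with two rules: rows apply by scheduled visit label, wherever the visit falls in its window; and the repeat FPG is tested against the threshold of the visit that triggered it.

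The cost is one row and one footnote, with no new visits or assays. The downside is that a few more patients may be rescued at Week 12. Row 1's lack of a matching Week 6 visit is a separate mismatch that this change does not resolve; it could be tidied in the same amendment.
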